NCT01911676 Translational Neuroscience Optimization of GlyT1 Inhibitor

Statistical Analysis Plan 5/28/2021

Statistical Analysis Plan:

All dependent measures were assessed for normality using normal probability plots. Descriptive statistics were calculated prior to analyses. Each dependent variable was analyzed using a mixed effects model with dose (placebo, low, high), visit (pre- vs. post-drug), their interaction and period (first or second) as main effect. Interactions involving period were also assessed but were dropped from the models for parsimony. Subject was the clustering factor and the best-fitting variance-covariance structure for the repeated measures in each model was selected based on Schwartz' Bayesian Criterion. Least square means and standard errors were calculated to describe the patterns of means for each outcome. Post-hoc mean comparisons were tested to explain significant effects in the models. Additionally, for each outcome effect slices for the interaction are reported although those should be interpreted with caution when there are no significant interactions.

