#### Aims:

- Aim #1:To test the efficacy of treatment with two doses of PF-03463275 (40 mg or 60 mg versus placebo) combined with CR to enhance cognitive function in chronic, stable, antipsychotic treated patients with schizophrenia as measured by the composite score on the MATRICS Consensus Cognitive Battery (MCCB).
- Aim #2: To test the efficacy of treatment of 40mg or 60mg controlled release PF-03463275 BID combined with Cognitive Remediation (CR) in reducing the deficits in LTP observed in schizophrenia.

**Background:** Schizophrenia is a chronic debilitating illness with a prevalence of approximately 1% in the general population worldwide, affecting over 3.0 million individuals in the US. The World Health Organization's Global Burden of Disease 2000 ranked schizophrenia as the fifth leading cause of years lived with a disability. Cognitive deficits, for which there are currently no proven treatments, contribute significantly to disability associated with schizophrenia. As stated by Thomas Insel, there is an urgent need to develop effective treatments for cognitive impairments of schizophrenia (CIAS) (6). The purpose of the current project is to employ translational neuroscience approaches to optimally evaluate the efficacy of the glycine transporter-1 inhibitor (GlyT1I), PF-03463275, that has not been fully tested and to thereby demonstrate its potential for efficacy in treating CIAS.

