measure to assess cognitive change in treatment studies. The battery includes alternate test forms for repeated administrations. The MCCB will be administered at baseline and follow-ups. Change on the MCCB composite score will be calculated to assess for the overall effect of treatment, with change in specific cognitive domains including verbal and visual learning and short-term/working memory examined as exploratory analyses.

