In addition to the compensation for each in-person visit, subjects will be compensated \$5 for completing each compliance monitoring or CAROMA visit by phone. CAROMA visits will only be completed on weekdays that the research clinic is open. Subjects may earn up to \$350 dollars for completing all possible CAROMA visits.

TABLE 1:Substudy 2 Procedures																		
	Screen		eline eeks)	Period 1 (5 weeks)					Washout (3 weeks)			Follow - Up						
Week	Screen	-2	-1	0	1	2	3	4	5	6	7	8	9	10	11	12	13	14
Day		-14	-7	0	7	14	21	28	35	42	49	56	63	70	77	84	91	98
SCID	Х																	
WTAR	х																	
Psych Evaluation	х																	
Physical	Х																	
Genotyping	Х																	
Randomizat ion				х								х						
PF v Placebo				х	х	х	х	Х	х			х	х	х	х	х	х	
CR					х	х	х	х	Х				х	х	х	х	х	
PANSS				х		Х		х				х		Х		х		
SGI				х		Х		Х	Х			х		х		х	Х	
PAOFI				Х		Х		Х	Х			Х		Х		х	Х	
Movement Exam				х		х		х				х		х		х		
MCCB		Х								Х								Х
LTP				Х					Х			Х					Х	
PK				Х	Х	Х	Х	Х	Х			Х	Х	Х	Х	Х	Х	
BDNF				х														
СВС	Х			х		Х		Х				х		х		Х		
CMP	Х			х		Х		х				х		Х		Х		
ECG	х			х		Х		х				Х		Х		Х		
Utox	х	Х	Х	Х		х		Х		Х	Х	Х		Х		Х		

SCID: Structured Clinical Interview for DSM IV; WTAR: Wechsler Test of Adult Reading; CBC: Complete Blood Count; CMP: Comprehensive Metabolic Panel; ECG: Electrocardiogram; Utox: Urine Toxicology screen; CR: Cognitive Remediation; PANSS: Positive and Negative Syndrome Scale; Sensory Gating Inventory; PAOFI: Patient Assessment of Own Functioning Inventory; LTP: Long Term Potentiation; BDNF: Brain Derived Neurotrophic Factor. Per P.I. discretion, study procedures may be repeated, and the duration of participation may be extended to account for scheduling conflicts and extenuating circumstances. Thus, the number of weeks listed per period may vary.

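### For the MCCB, the SAP's dose-by-visit interaction fits separate pre-drug means that randomisation has already made equal, which adds avoidable noise; how much depends on a coding the SAP does not state

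*SAP*

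**What the plan says.** The SAP is one paragraph and applies one mixed model to every dependent variable: "dose (placebo, low, high), visit (pre- vs. post-drug), their interaction and period (first or second) as main effect". Subject is the cluster. On period it says: "Interactions involving period were also assessed but were dropped from the models for parsimony". On covariance: "the best-fitting variance-covariance structure for the repeated measures in each model was selected based on Schwartz' Bayesian Criterion". It names no primary contrast. Post-hoc comparisons serve to explain significant effects, and "for each outcome effect slices for the interaction are reported although those should be interpreted with caution when there are no significant interactions".

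Aim 1 of the protocol is judged on the MCCB composite. The protocol's MCCB paragraph says "The MCCB will be administered at baseline and follow-ups" and "Change on the MCCB composite score will be calculated to assess for the overall effect of treatment". In the procedures table ("TABLE 1:Substudy 2 Procedures") the MCCB is marked at Weeks -2, 6 and 14 only, and randomisation at Weeks 0 and 8. LTP is marked at Weeks 0, 5, 8 and 13, so it has a pre and a post value in each period; the MCCB does not.

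The Research Design and Randomization sections describe a within-subject design. Each patient takes placebo in one period and one of the two active doses in the other.

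**The concern.** A dose main effect plus a dose-by-visit interaction gives each dose a free pre-drug mean. The interaction for 40 mg is then (40 mg minus placebo, post-drug) minus (40 mg minus placebo, pre-drug). Week -2 precedes allocation, so for the MCCB the second bracket has expectation zero. Estimating and subtracting it adds variance and removes no bias.

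The informative comparison is Week 6 against Week 14 in the same patient, which is the reason for a crossover. If the interaction decides whether an effect is declared, a real cognitive effect could be missed through noise that the design makes unnecessary.

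**Working it through.** The documents give no sample size, SD, correlation, alpha or power, so there is no figure to reproduce.

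**Inputs**
- From the documents: the model terms (SAP), MCCB at Weeks -2, 6 and 14 (procedures table), and placebo plus one dose per patient (Randomization section).
- Assumed: sequences placebo-40, 40-placebo, placebo-60 and 60-placebo in equal numbers; equal variance σ² at each occasion; constant correlation r of 0.5 to 0.9; no carry-over (the SAP's model has no such term either).

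**Comparator.** The same three scores with one common pre-drug mean, three post-drug dose means and period. Generalised least squares gives, for 40 mg versus placebo,

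N·Var/σ² = (1−r)(3+4r)/(1+r).

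At r = 0.8 this is 0.2 × 6.2/1.8 = 0.689.

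**Coding A: each score entered once.** The mechanism can be checked by hand with one dose and two sequences. The post-drug part has variance 2(1−r)σ²/N. The pre-drug difference compares the two sequence groups and, after adjustment for the post-drug scores, has variance 4(1−r)(1+2r)σ²/[(1+r)N]. The ratio to the comparator is therefore 1 + 2(1+2r)/(1+r), which is 3.89 at r = 0.8. With all four sequences, least squares gives:

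| r | Interaction, N·Var/σ² | Common pre-mean | Ratio |
|---|---|---|---|
| 0.5 | 5.314 | 1.667 | 3.19 |
| 0.7 | 3.301 | 1.024 | 3.23 |
| 0.8 | 2.232 | 0.689 | 3.24 |
| 0.9 | 1.130 | 0.347 | 3.25 |

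A simulation at r = 0.8 gave 3.23. With 20% dropout the ratio is 2.82 to 2.83. If correlation decays as AR(1) with parameter 0.5 to 0.9, it is 3.11 to 3.81.

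**Coding B: Week -2 copied as the pre score of both periods.** In one patient (y14 − y−2) − (y6 − y−2) = y14 − y6, so the baseline cancels. The true variance is 4(1−r)σ²/N, and the ratio is 4(1+r)/(3+4r): 1.20 at r = 0.5 and 1.15 at r = 0.9. A compound-symmetry model with correlation r that treats the copy as new data reports 6(1−r)σ²/N, a ratio of 1.80 to 1.73. If its correlation instead rises to (5r+1)/6 because of the duplicate, it reports 1.50 to 1.44.

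**Coding C: Week 6 as the Period 2 pre score.** The within-patient contrast is y14 − 2·y6 + y−2, with the sign reversed for active-first patients. For a drug effect d its mean is d in placebo-first patients and 2d in active-first patients, because Week 6 then carries the drug effect twice. The average is 1.5d. In the four-sequence model the contrast estimates 1.25 times the 40 mg effect if 60 mg is inert, and 1.5 times if the doses are equally effective. The true variance is 8(1−r)σ²/N, a ratio of 2.40 to 2.30. The same compound-symmetry model reports 6(1−r)σ²/N, which is too small.

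**Post-drug slice.** Under coding A, the SAP's own comparison of 40 mg with placebo at the post-drug visit has a ratio of 1.02 to 1.05.

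**Power, coding A only** (assumed N = 40, r = 0.8, two-sided 0.05). The SEs are √(2.232/40) = 0.236 SD and √(0.689/40) = 0.131 SD. Power is Φ(effect/SE − 1.96). For 0.4 SD this gives Φ(−0.27) = 39% versus Φ(1.09) = 86%. For 0.3 SD it gives 25% versus 63%.

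**The case against.** The strongest reply is that the factor of about three belongs to one coding and not to the SAP. The protocol speaks of a baseline and follow-ups and of change scores, which may well mean one Week -2 baseline serving both periods (coding B). The true loss is then 15 to 20%, and it is largely untrue that different patients are being compared. This stands: a reader might infer from the model sentence alone that the variance is always tripled, and the documents do not support that.

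Nor can one say that the coding makes little difference. Under coding C the main fault is bias. Dividing by the squared inflation brings the ratio down to between 2.30/1.5² = 1.02 and 2.40/1.25² = 1.54, so that coding is not a case of threefold noise.

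A second reply is that the SAP reports slices for each outcome, that the post-drug slice is nearly efficient, and that the interaction is never named as the Aim 1 test. This also stands. A reader might infer that the crossover's within-patient precision is lost, but a good estimate would still be reported. What remains is that the SAP's only rule of interpretation places that estimate beneath the interaction.

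A third reply is that the SAP is written in the past tense, so changing the contrast may be post hoc. That affects how the fix must be labelled.

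**Conclusion.** The concern holds in conditional form. For the MCCB, the separate pre-drug means are unnecessary because the only drug-free score precedes randomisation. No coding examined makes the interaction as good a test as a post-drug contrast with a common pre-drug mean. The variance ratio is about 3.2 with each score entered once, and 1.15 to 1.20 (reported 1.73 to 1.80) with Week -2 copied. With Week 6 as the Period 2 pre score it is 2.3 to 2.4, with a contrast 1.25 to 1.5 times the 40 mg effect and an understated variance.

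These figures rest on four equal sequences and constant correlation of 0.5 to 0.9. The ratios do not depend on N. The reported variances also assume compound symmetry, whereas the SAP leaves the structure to a fit criterion. The 39% versus 86% power comparison applies only to coding A with the assumed N, correlation and 0.4 SD effect; it is not an estimate of this trial's power. A non-significant interaction alone should not be read as evidence of no drug effect.

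**What to change.** **MCCB.** State in the SAP that Weeks -2, 6 and 14 each enter once. Fit occasion (three levels) plus 40 mg and 60 mg effects at Weeks 6 and 14, with subject as cluster and one common Week -2 mean. A near-equivalent is to model Weeks 6 and 14 on dose and period with the Week -2 composite as covariate. Test Aim 1 by the post-drug contrasts of 40 mg and 60 mg with placebo.

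**LTP.** Treat it separately. Its Week 8 value follows Period 1 treatment, so equal pre-drug means should not be imposed there. Use each period's pre-drug LTP as covariate for the post-drug value, and keep the dose-by-visit contrast as a sensitivity analysis, because a lasting Period 1 effect would be only partly adjusted.

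**Cost.** A short SAP addition and changed model statements; no new data. For the MCCB, randomisation justifies the common mean. If results are already known, label the analysis as a re-analysis and report the SAP's interaction beside it, together with the coding actually used.
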